4.2. Overall Study Duration

Participants will be on-study for a duration of up to 60 weeks (if not participating in the LTE), or 108 weeks (if participating in the LTE), as follows: screening, up to 30 days; placebo-controlled period, 16 weeks; OLE period, 36 weeks; LTE period, 48 weeks; and a 28-day (+ 7 days) safety follow-up.

The study begins when the first participant (or guardian or legally authorized representative) signs the ICF. The end of the study is defined as the date of the last visit of the last participant in the study or the last scheduled procedure shown in the SoA for the last participant in the study.

A participant who does not continue into the LTE period is considered to have completed the study if he/she has completed both the placebo-controlled period and the OLE period of the study, including the last visit or the last scheduled procedure shown in the SoA. A participant who continues into the LTE period is considered to have completed the study if he/she has completed the placebo-controlled; OLE and LTE periods of the study, including the last visit or the last scheduled procedure shown in the SoA (see Table 3).

4.3. Study Termination

The investigator retains the right to terminate study participation at any time, according to the terms specified in the study contract. The investigator is to notify the IRB/IEC of the study's completion or early termination, send a copy of the notification to the sponsor or sponsor's designee, and retain 1 copy for the site study regulatory file.

The sponsor may terminate the study electively if, for example, required by regulatory decision. If the study is terminated prematurely, the sponsor will notify the investigators, the IRBs and IECs, and the regulatory bodies of the decision and reason for termination of the study.

5. STUDY POPULATION

The study population will include men and women aged 18 to 75 years who have had a diagnosis of HS (Hurley Stage I, II, or III) for at least 3 months and who have at least a 5 AN count at screening and baseline with inflammatory lesions that affect at least 2 distinct anatomical areas.

Deviations from eligibility criteria are not allowed because they can potentially jeopardize the scientific integrity of the study, regulatory acceptability, and/or participant safety. Therefore, adherence to the criteria as specified in the Protocol is essential. Prospective approval of Protocol deviations to recruitment and enrollment criteria, also known as Protocol waivers or exemptions, are not permitted.

5.1. Inclusion Criteria

Participants are eligible to be included in the study only if all of the following criteria apply:

- 1. Men and women age 18 to 75 years inclusive at the time of signing the ICF.
- 2. HS disease duration of at least 3 months before screening.
- 3. Diagnosis of HS defined as:
 - a. A total of at least 5 inflammatory lesions (AN) at screening AND baseline AND
 - b. Inflammatory lesions present in at least 2 distinct anatomical areas
- 4. Willingness to avoid pregnancy or fathering children based on the criteria below.
 - a. Male participants with childbearing potential must agree to take appropriate precautions to avoid fathering children (with at least 99% certainty) from screening through 90 days after the last dose of study drug and must refrain from donating sperm during this period. Permitted methods that are at least 99% effective in preventing pregnancy (see Appendix A) should be communicated to the participants and their understanding confirmed.
 - b. Female participants with childbearing potential must have a negative serum pregnancy test at screening and must agree to take appropriate precautions to avoid pregnancy (with at least 99% certainty) from screening through safety follow-up. Permitted methods that are at least 99% effective in preventing pregnancy (see Appendix A) should be communicated to the participants and their understanding confirmed.
 - c. Female participants without childbearing potential (ie, surgically sterile with a hysterectomy and/or bilateral oophorectomy OR postmenopausal, defined as amenorrhea ≥ 12 months prior to screening), confirmed by FSH levels at screening, are eligible.
- 5. Participants agree NOT to use topical antiseptics (see Section 6.6.2) on the areas affected by HS lesions during the placebo-controlled 16-week treatment period.
- 6. For Germany only, participants must have a history of inadequate response or intolerance to an adequate course of oral antibiotics for treatment of HS, as assessed by the investigator through study participant interview and review of medical history.

5.2. Exclusion Criteria

Participants are excluded from the study if any of the following criteria apply:

- 1. Inability of the participant (or guardian or legally authorized representative) to comprehend the ICF or unwillingness to sign the ICF.
- 2. Presence of > 20 draining fistulas at screening or baseline.
- 3. Women who are pregnant (or who are considering pregnancy) or lactating.
- 4. Participants with concurrent conditions or history of other diseases, as follows:
 - a. Thrombocytopenia, coagulopathy, or platelet dysfunction.
 - b. Any clinically significant medical condition other than HS, as determined by the investigator, that is not adequately controlled with appropriate treatment OR may interfere with the course, severity, or assessments of HS.
 - c. Any other active skin disease or condition (eg, bacterial, fungal, or viral infection) that may interfere with the course, severity, or assessments of HS.
 - d. Active systemic viral infection or any active viral infection that, based on the investigator's clinical assessment, makes the participant an unsuitable candidate for the study.
 - e. Current herpes zoster infection, a history of disseminated herpes simplex, or a history of herpes zoster.
 - f. History of malignancy, including lymphoma and leukemia within 5 years before baseline, other than a successfully treated nonmetastatic cutaneous squamous cell carcinoma, basal cell carcinoma, or localized carcinoma in situ of the cervix.
 - g. Albinism.

CONFIDENTIAL

6. Prolonged QTcF, defined as \geq 450 milliseconds.

Note: Prolonged QTcF values of \geq 450 milliseconds at screening are to be confirmed by performing 2 additional ECGs and averaging the results to determine if the averaged value meets the exclusion criterion.

- 7. Have evidence of active or latent or inadequately treated infection with *Mycobacterium tuberculosis* (ie, TB) as defined by the following:
 - A positive QuantiFERON[®]-TB Gold In-Tube test (QFT-GIT) or positive Mantoux/PPD tuberculin skin test (if appropriate, per Section 8.3.6) performed at or within the 12 weeks prior to Day 1 is exclusionary; a negative test is required for eligibility. It is recommended that participants with a history of Bacille Calmette Guérin vaccination be tested with the QFT-GIT, since the Mantoux/PPD tuberculin skin test may be positive due to vaccination. See Section 8.3.6 for requirements for Mantoux/PPD tuberculin skin testing. A QFT-GIT or Mantoux/PPD tuberculin skin test is not required if the participant has previously received a documented adequate course of therapy for either latent or active TB infection.
 - A history of either untreated or inadequately treated latent or active TB infection.
- If a participant has previously received an adequate course of therapy for either latent (9 months of isoniazid in a locale where rates of primary multidrug TB resistance are < 5% or an acceptable alternative regimen) or active (acceptable multidrug regimen) TB infection, neither a QFT-GIT nor a Mantoux/PPD tuberculin skin test is needed, but a chest radiograph(s), performed within 3 months of Day 1, is required. To be considered eligible for the study, the radiograph(s) must be negative for active tuberculosis infection as determined by a qualified radiologist. Documentation of adequate treatment for TB and negative chest radiograph(s) results must be obtained prior to Day 1.
- A participant who is currently being treated for active TB infection is to be excluded.
- 8. Participants known to be infected with HIV, hepatitis B, or hepatitis C (see Table 10).
- 9. Decreased blood cell counts at screening, defined as follows:
 - a. Leukocytes $< 3.0 \times 10^{9}/L$ ($< 2.5 \times 10^{9}/L$ for African-American participants).
 - b. ANC $< 1.5 \times 10^{9}$ /L.
 - c. Lymphocytes $< 0.8 \times 10^9$ /L.
 - d. Hemoglobin < 9 g/dL.
 - e. Platelet count $< 150 \times 10^9$ /L.
- 10. Severely impaired liver function (Child-Pugh Class C) or ALT or AST levels $\geq 2 \times ULN$ or total bilirubin $\geq 2 \times ULN$, unless due to Gilbert's syndrome.
- 11. Impaired renal function with serum creatinine > 1.5 mg/dL.
- 12. Known hypersensitivity or severe reaction to INCB054707 or excipients of INCB054707 (refer to the IB).
- 13. Known history of clinically significant drug or alcohol abuse in the last year prior to baseline.
- 14. Inability or unlikeliness of the participant to comply with the dose schedule and study evaluations, in the opinion of the investigator.
- 15. Any other condition that would, in the investigator's judgment, interfere with full participation in the study, including administration of study drug and attending required study visits; pose a significant risk to the participant; or interfere with interpretation of study data.
- 16. The following patients are excluded in France: vulnerable populations according to article L.1121-6 of the French Public Health Code and adults under legal protection or who are unable to express their consent per article L.1121-8 of the French Public Health Code.

5.3. Lifestyle Considerations

No lifestyle restrictions are required for this study; however, nicotine and alcohol use will be evaluated as indicated in the SoA (see Table 3). Additional information regarding nicotine and alcohol use data collection is provided in the Study Manual.

5.4. Screen Failures

Screen failures are defined as participants who consent to participate in the clinical study but are not subsequently randomly assigned to study treatment.

Tests with results that fail eligibility requirements may be repeated once during screening if the investigator (or designee) believes that the participant would be eligible if retested. Additionally, a participant who fails screening may repeat the screening process 1 time if the investigator (or designee) believes that there has been a change in eligibility status. Participants who are rescreened must reconsent and be assigned a new participant number.

5.5. Replacement of Participants

Participants may be replaced at any time during this study, at the discretion of the medical monitor or designee.

5.6. Data Monitoring Committee

An internal DMC will be established to provide independent oversight of the study. The primary responsibility of the DMC will be to ensure the safety of study participants. The specific responsibilities of the DMC will be detailed in a separate DMC charter.

6. STUDY TREATMENT

6.1. Study Treatments Administered

Information regarding study drug and administration is provided in Table 6. Participants will record study drug administration in a daily diary. Further information regarding treatment administration is provided in Appendix B.

6.2. Preparation, Handling, and Accountability

The investigator or designee must confirm appropriate temperature conditions have been maintained during transit for all study treatments received and any discrepancies are reported and resolved before use of the study treatment.

Only participants enrolled in the study may receive study treatment, and only authorized site staff may supply or administer study treatment. All study treatment must be stored in a secure, environmentally controlled, and monitored (manual or automated) area in accordance with the labeled storage conditions with access limited to the investigator and authorized site staff.

The investigator (or designee) is responsible for study treatment accountability, reconciliation, and record maintenance (ie, receipt, reconciliation, and final disposition records). Inventory and accountability records must be maintained and readily available for inspection by the study monitor and are open to inspection at any time by any applicable regulatory authorities. The investigator or designee must maintain records that document:

- Delivery of study drugs to the study site.
- Inventory of study drugs at the site.
- Participant use of the study drugs, including pill counts from each supply dispensed.
- Return of study drugs to the investigator or designee by participants.

The investigational product must be used only in accordance with the Protocol. The investigator will also maintain records adequately documenting that the participants were provided the specified study drug. These records should include dates, quantities, and any available batch or serial numbers or unique code numbers assigned to the investigational product and study participants.

Completed accountability records will be archived by the site. The investigator or designee will be expected to collect and retain all used, unused, and partially used containers of study drug until verified by the study monitor (unless otherwise agreed to by the sponsor). At the conclusion of the study, the investigator or designee will oversee shipment of any remaining study drug back to the sponsor or its designee for destruction according to institutional SOPs. If local procedures mandate on-site destruction of the investigational supply, the site should (where local procedures allow) maintain the investigational supply until the study monitor inspects the accountability records in order to evaluate compliance and accuracy of accountability by the investigative site. At sites where the study drug is destroyed before monitor inspection, the monitors rely on documentation of destruction per the site SOP.

Further guidance and information for the final disposition of unused study treatments are provided in the Study Manual.

6.3. Measures to Minimize Bias: Randomization and Blinding

Randomization to treatment in the double-blind period of the study will occur centrally via the IRT system (see Section 8.1.3). Participant randomization will be stratified based on geographical region (North America and outside of North America) and disease severity (Hurley

Stages I, II, and III) with no more than 25% of the total number of participants as Hurley Stage III. Full details for randomization will be provided in the Study Manual.

Participants, investigators, and the sponsor will be blinded to each participant's initial treatment assignment for the double-blind treatment period. Emergency unblinding will occur if an AE requires the investigator to be made aware of the participant's treatment assignment (see emergency unblinding procedures in Section 9.5).

During the 36-week open-label treatment period, participants will receive INCB054707 75 mg QD. During the LTE period (also open label), participants will receive INCB054707 up to 75 mg QD, with the possibility of dose change and dose decrease, as described in Section 6.5.1.

6.4. Study Treatment Compliance

Compliance with all study-related treatments should be emphasized to the participant by the site personnel, and appropriate steps should be taken to optimize compliance during the study. Compliance with study drug will be calculated by the sponsor based on the drug accountability (eg, tablet counts) documented by the site staff and monitored by the sponsor/designee. Participants will be instructed to bring all unused study drugs with them to the study visits in order for site personnel to conduct tablet counts to assess study drug accountability. The drug accountability documentation will be used by the sponsor to calculate treatment compliance.

6.5. Dose Modifications

6.5.1. Criteria and Procedures for Dose Interruptions and Adjustments of Study Drug

Safety concerns should be discussed with the sponsor immediately upon occurrence or awareness to determine if the participant should continue or discontinue study treatment.

No dose modifications will be allowed during the placebo-controlled period. In some circumstances, it may be necessary to temporarily interrupt study treatment as a result of AEs or laboratory abnormalities that have an unclear relationship to the study drug (see Table 7).

Except in cases of emergency, it is recommended that any laboratory findings be confirmed and that the investigator consult with the sponsor medical monitor (or designee) before temporarily interrupting study drug. Participants who experience a recurrence of the AEs or laboratory abnormalities upon restarting the study drug at the previously administered dose may have the study drug permanently discontinued.

Version 2

6.5.2. Criteria for Permanent Discontinuation of Study Drug

The occurrence of unacceptable severity of an AE not caused by the underlying disease will be presumed to be related to study drug treatment and will require that the study drug be permanently discontinued. Unacceptable severity is defined as follows:

- The occurrence of an AE that is related to study drug that, in the judgment of the investigator or the sponsor's medical monitor (or designee), compromises the participant's ability to continue study-specific procedures or is considered to not be in the participant's best interest.
- Participant presents with a worsening of HS that requires treatment with a prohibited concomitant medication.

Additionally, study drug will be discontinued as outlined in Section 6.5.1 and Section 6.6.4.

See Section 7 for discontinuation procedures.

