7. DISCONTINUATION OF STUDY TREATMENT AND PARTICIPANT WITHDRAWAL

7.1. Discontinuation of Study Treatment

7.1.1. Reasons for Discontinuation

Participants **must** be discontinued from study treatment for the following reasons:

- The participant becomes pregnant.
- Consent is withdrawn.

Note: Consent withdrawn means that the participant has explicitly indicated that he/she does not want to be followed any longer; in this case no further data, except data in public domain, may be solicited from or collected on the participant. Participants may choose to discontinue study treatment and remain in the study to be followed for safety monitoring.

- Further participation would be injurious to the participant's health or well-being, in the investigator's (or designee) medical judgment.
- Any adverse event of unacceptable severity as noted in Section 6.5.
- Participant meets discontinuation criteria as described in Section 6.6.4.
- The study is terminated by the sponsor.
- The study is terminated by the local health authority, IRB, or IEC.

A participant **may** be discontinued from study treatment as follows:

- If, during the course of the study, a participant is found not to have met eligibility criteria, the medical monitor, in collaboration with the investigator, will determine whether the participant should be withdrawn from study treatment.
- If a participant is noncompliant with study procedures or study drug/treatment administration in the investigator's opinion, the sponsor should be consulted for instruction on handling the participant.

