9.1. Definition of Adverse Event

Adverse Event Definition

- An AE is any untoward medical occurrence associated with the use of a drug in humans, whether or not considered drug-related.
- An AE can therefore be any unfavorable and unintended sign (including an abnormal laboratory finding), symptom, or disease (new or exacerbated) temporally associated with the use of study treatment.

Events Meeting the Adverse Event Definition

- Any safety assessments (eg, ECG, vital signs measurements), including those that worsen from baseline, considered clinically significant in the medical and scientific judgment of the investigator (ie, not related to progression of underlying disease).
- Abnormal laboratory test results constitute an AE if they are considered clinically meaningful, induce clinical signs or symptoms, require concomitant therapy, or require changes in study drug. Whenever possible, a diagnosis (eg, anemia, thrombocytopenia) should be recorded in the eCRF rather than the abnormal laboratory test result (eg, low hemoglobin, platelet count decreased).
- Exacerbation of a chronic or intermittent pre-existing condition including either an increase in frequency and/or intensity of the condition.
- New conditions detected or diagnosed after study treatment administration even though they may have been present before the start of the study.
- Signs, symptoms, or the clinical sequelae of a suspected drug-drug interaction.
- Signs, symptoms, or the clinical sequelae of a suspected overdose of either study treatment or a concomitant medication. Overdose per se will not be reported as an AE/SAE unless it is an intentional overdose taken with possible suicidal/self-harming intent. Such overdoses should be reported regardless of sequelae.
- "Lack of efficacy" or "failure of expected pharmacological action" per se will not be reported as an AE or SAE. Such instances will be captured in the efficacy assessments. However, the signs, symptoms, and/or clinical sequelae resulting from lack of efficacy will be reported as an AE or SAE if they fulfill the definition of an AE or SAE.

Events **NOT** Meeting the Adverse Event Definition

- Any clinically significant abnormal laboratory findings or other abnormal safety assessments that are associated with the underlying disease, unless judged by the investigator to be more severe than expected for the participant's condition.

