- The disease/disorder being studied or expected progression, signs, or symptoms of the disease/disorder being studied, unless more severe than expected for the participant's condition or considered to be treatment-related by the investigator.
- Efficacy endpoints as outlined in Section 3 will not be reported as AE/SAEs, specifically, any event that is related to disease progression of the disease under study. Unblinded aggregated efficacy endpoint events and safety data will be monitored to ensure the safety of the participants in the study. Any suspected endpoint that upon review is not progression of the disease under study will be forwarded to Incyte Pharmacovigilance as an SAE within 24 hours of determination that the event is not progression of the disease under study.

- Medical or surgical procedure (eg, endoscopy, appendectomy): the condition that leads to the procedure is the AE if it occurred after signing informed consent. If present before entering the study, the condition should be captured as medical history.
- Situations in which an untoward medical occurrence did not occur (social and/or convenience admission to a hospital).
- Anticipated day-to-day fluctuations of pre-existing disease(s) or condition(s) present or detected at the start of the study that do not worsen.

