#### 9.2.2. Adverse Event Summaries

AE will be summarized by treatment groups for the safety population in the PC period, the open-label evaluable population in the OLE period, participants who take INCB054707 75 mg throughout study participation up to Week 52, and the long-term evaluable population in the LTE period.

An overall summary of AEs will include the following:

- Number (%) of participants reporting any TEAEs
- Number (%) of participants reporting any serious TEAEs
- Number (%) of participants reporting any Grade 3 or higher TEAEs
- Number (%) of participants reporting any treatment-related TEAEs
- Number (%) of participants who temporarily interrupted study treatment because of TEAEs
- Number (%) of participants who permanently discontinued study treatment because of TEAEs
- Number (%) of participants who had a fatal TEAE

The following summaries will be produced by MedDRA term (if 10 or fewer subjects appear in a table, a listing may be appropriate):

- Summary of TEAEs by MedDRA SOC and PT
- Summary of TEAEs by MedDRA PT in decreasing order of frequency
- Summary of TEAEs by MedDRA SOC, PT, and maximum severity
- Summary of TEAEs by MedDRA SOC, PT, and CTCAE grade category
- Summary of Grade 3 or higher TEAEs by MedDRA SOC and PT
- Summary of Grade 3 or higher TEAEs by MedDRA PT in decreasing order of frequency
- Summary of serious TEAEs by MedDRA SOC and PT
- Summary of serious TEAEs by MedDRA PT in decreasing order of frequency
- Summary of treatment-related TEAEs by MedDRA SOC and PT
- Summary of treatment-related TEAEs by MedDRA PT in decreasing order of frequency
- Summary of Grade 3 or higher treatment-related TEAEs by MedDRA SOC and PT

- Summary of treatment-related serious TEAEs by MedDRA SOC and PT
- Summary of TEAEs with a fatal outcome by MedDRA SOC and PT
- Summary of TEAEs leading to dose reduction by MedDRA SOC and PT
- Summary of TEAEs leading to dose interruption by MedDRA SOC and PT
- Summary of TEAEs leading to discontinuation of study drug by MedDRA SOC and PT
- Summary of TEAEs requiring concomitant medications by MedDRA SOC and PT

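### Protocol 6.5.2 defines an AE not caused by HS partly by worsening of HS, so by-arm discontinuations because of TEAEs can mix lack of efficacy with tolerability

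*Protocol*

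**What the plan says.** Protocol 6.5.2 opens with the rule that "The occurrence of unacceptable severity of an AE not caused by the underlying disease will be presumed to be related to study drug treatment" and makes permanent discontinuation mandatory. It then defines unacceptable severity by two bullets. The first is a related AE that, in the judgment of the investigator or medical monitor, compromises continued participation or is against the participant's interest. The second is "Participant presents with a worsening of HS that requires treatment with a prohibited concomitant medication".

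Protocol 7.1.1, listing the reasons for which treatment must stop, includes "Any adverse event of unacceptable severity as noted in Section 6.5". Stops under the rescue rules of 6.6.4 have their own line. The list has no line for worsening of HS or lack of efficacy.

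Protocol 9.1 takes a different approach to the same kind of event:
- Lack of efficacy "per se will not be reported as an AE or SAE. Such instances will be captured in the efficacy assessments". Signs, symptoms and sequelae of it are AEs if they meet the AE definition.
- The study disease and its expected progression are not AEs, "unless more severe than expected for the participant's condition or considered to be treatment-related by the investigator".
- Efficacy endpoints "will not be reported as AE/SAEs, specifically, any event that is related to disease progression of the disease under study". This bullet does not repeat the exception.
- Exacerbation of a chronic pre-existing condition is listed among events that are AEs.

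SAP 9.2.2 reports, by treatment group, "Number (%) of participants who permanently discontinued study treatment because of TEAEs", and tabulates TEAEs leading to discontinuation by system organ class and preferred term. It gives no rule for stops caused by worsening of HS.

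**The concern.** A participant who deteriorates and needs a prohibited treatment is, on the face of it, an efficacy failure. Read as written, 6.5.2 and 7.1.1 place that participant under an adverse-event heading; the general rule in 9.1 does not. The situation need not be rare: Protocol 6.6.3 prohibits biologics, most systemic immunosuppressants and conventional therapies that could affect HS, so many escalations for treatment failure could meet the second bullet.

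The study is meant to support the choice of one regimen for Phase 3 (Protocol 2.1.2). Discontinuation because of TEAEs is one of the usual tolerability measures compared across doses. If some of those stops are efficacy failures, and sites do not sort them the same way, differences between arms in that line no longer describe tolerability alone.

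**Working it through.** **The wording.** Three questions can be put to each section about a stop for worsening of HS that needs a prohibited medication.

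| | Is it an AE? | Caused by HS? | Related to study drug? |
|---|---|---|---|
| 6.5.2 | Yes: it defines an AE of unacceptable severity | No, by the lead-in | Presumed yes |
| 7.1.1 | Yes: it refers back to 6.5 under an adverse-event label | Not stated | Not stated |
| 9.1 | Generally no; yes if more severe than expected, judged treatment-related, or a sequela that itself meets the AE definition | Treated as progression of the disease | Left to the investigator |

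The 6.5.2 row cannot be satisfied: worsening of HS cannot be something that HS did not cause. The first column also differs between sections, and 9.1 is itself conditional, so careful readers could reach different answers for one participant.

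**What reaches the tables.** The count of participants who stopped because of TEAEs depends on whether the stop is recorded as an AE. The treatment-related rate does not depend on the 6.5.2 presumption: Protocol 10.4.3 and SAP 9.2.1 both take the investigator's attribution and count a missing attribution as related. Protocol 9.3 asks for a judgment on each event, based on positive evidence or argument. The related rate moves only if an investigator carries the presumption into that judgment or leaves the field empty.

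**Size.** The documents give no figure to reproduce. The only input is arm size (SAP 3.1): 200 / 4 = 50 per arm. One participant is 1/50 = 2 percentage points.

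Let t be the true rate of tolerability stops in an arm and w the rate of HS-worsening stops recorded as AEs. The reported rate is t + w, and the reported difference is (t_active − t_placebo) + (w_active − w_placebo). All rates below are assumptions. Take t = 4% on placebo (2/50) and 8% on active (4/50), a true difference of +4 points.

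| w placebo | w active | Reported placebo | Reported active | Difference |
|---|---|---|---|---|
| 0% | 0% | 4% (2/50) | 8% (4/50) | +4 |
| 4% | 4% | 8% (4/50) | 12% (6/50) | +4 |
| 6% | 2% | 10% (5/50) | 10% (5/50) | 0 |
| 10% | 4% | 14% (7/50) | 12% (6/50) | −2 |
| 20% | 8% | 24% (12/50) | 16% (8/50) | −8 |

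The difference is undisturbed when w is equal across arms, and is hidden or reversed when w is larger on placebo.

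The chance that an arm of 50 contains at least one such stop is 1 − (1 − w)^50: 39.5% at w = 1%, 63.6% at 2% and 92.3% at 5%.

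**The case against.** The best defence is that 6.5.2 is a stopping rule and not a recording rule. Protocol 8.3.1 says that the definition and recording of AEs are set out in Section 9, the HS bullet does not itself use the term AE, and a site that follows Section 9 may never code from 6.5.2. If the event is coded as an AE, the preferred-term tables in SAP 9.2.2 would show it in its own row, and SAP 6.2 separately summarises the primary reason for discontinuation. The eCRF reason list is not in the documents and may already include lack of efficacy. Some efficacy failures also leave by another route: more than 2 rescue interventions in the placebo-controlled period forces withdrawal (6.6.4.2), which 7.1.1 lists apart from the AE reason.

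Much of this stands, and it limits the consequence to what can happen. It does not remove the contradiction. Section 7.1.1 governs the reason for stopping, and it carries 6.5 forward under an adverse-event label. Preferred-term rows show only the cases that sites chose to record as AEs, and the overall count does not separate them.

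Three stronger inferences are tempting and are not supported. First, a reader might infer that treatment-related AE rates are inflated because 6.5.2 presumes relatedness; the analysis definition uses investigator attribution. Second, a reader might take 9.1 as a flat exclusion of HS worsening; its exceptions could make some of these events AEs under 9.1 as well. Third, a reader might apply the 27% to 50% lack-of-efficacy dropout cited in Protocol 2.1.2; that comes from earlier studies and does not estimate how many stops here would be coded as AEs.

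**Conclusion.** The point holds in a limited form. Protocol 6.5.2 contradicts itself, 7.1.1 carries the contradiction into the reasons for stopping, and 9.1 generally points the other way. The by-arm count of participants who discontinued because of TEAEs can therefore mix lack of efficacy with tolerability, at 2 percentage points per affected participant in an arm of about 50.

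Whether this distorts the comparison, and in which direction, depends on how many such stops occur, how they divide between arms and how sites record them. None of these is given. More HS worsening on placebo or the lowest dose is plausible but assumed, and the scenario table rests on assumed rates throughout. It would go too far to say that the by-arm rates cannot be interpreted. The primary and key secondary endpoints are built from lesion counts and do not depend on AE coding. The change is worth making because it is cheap and the line affected is a tolerability comparison between doses.

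**What to change.** Reconcile Protocol 6.5.2, 7.1.1 and 9.1 on whether, and when, worsening of HS is an AE. The stopping criterion itself stays as the sponsor intends; only its classification needs to change.

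- In 6.5.2, take the HS-worsening bullet out of the definition of an AE not caused by the underlying disease, and so out of the presumption of relatedness. State it as a separate criterion.
- In 7.1.1, list worsening of HS or lack of efficacy as its own reason, and add it to the eCRF reason list if it is not already there.
- Add a cross-reference to 9.1, so that sites know Section 9 alone decides whether the event is also recorded as an AE.
- In SAP 9.2.2, show TEAEs leading to discontinuation by arm with and without HS preferred terms, with the list of terms fixed before unblinding.

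The cost is a few sentences in the protocol, possibly one eCRF reason code, one extra display, and possible queries on records already entered.
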